We will enroll menthol (n = 125) and non-menthol (n = 125) YA smokers who initiated regular smoking in the past 12-months or who initiated regular smoking more than 12 months ago, and measure appeal/reinforcement for menthol and non-menthol cigarettes and the impact of appeal/reinforcement on changes in smoking (progression, nicotine dependence, and cigarette harm perceptions) at a 6-month follow-up. Appeal/reinforcement will be assessed via two complementary measurement paradigms: one in the laboratory using a well-validated behavioral economic choice task and the other in the natural environment using ecological momentary assessment (EMA). Laboratory studies provide a great deal of efficiency and internal control, allowing for causal inference of acute subjective response; while EMA allows for similar causal sequencing of behavior, but in an ecologically valid format in the smoker's natural environment. It is hypothesized that, compared to nonmenthol smokers, menthol smokers will show greater appeal/reinforcement, both in the laboratory and via EMA, and will be more likely to show progression to regular smoking, increases in nicotine dependence, and lower cigarette harm perceptions by a 6-month follow-up. The association between menthol preference and smoking outcomes will be reduced or non-significant after including measures of appeal/reinforcement in the model; suggesting that menthol's appeal/reinforcement accounts for smoking progression. This research will isolate the unique effects of menthol in smoking and will help inform regulatory decisions about the abuse liability of menthol cigarettes and the use of flavors in other tobacco products in future studies.

Specific Aims

Aim 1 (Phase 1): Examine the absolute and relative reinforcing value (appeal) of menthol vs. non-menthol cigarettes using a validated laboratory-based behavioral economic choice task.

Aim 2 (Phase 2): Examine the subjective effects (appeal) of menthol vs. non-menthol cigarettes (own brand) during 14 days of ecological momentary assessment (EMA) in the natural environment.

Aim 3 (Phase 3): Examine the degree to which laboratory (Phase 1) and EMA (Phase 2) measurements of menthol appeal/appeal causally impact (i.e., mediate) the association between menthol brand preference at baseline and 6-month smoking outcomes (progression, increased nicotine dependence, lower cigarette harm perceptions).

Study Design

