In addition to the aforementioned recruitment methods, we will use BuildClinical, who will assist with recruitment by designing and managing targeted, GCP-compliant, IRB approved advertising. **BuildClinical** is a data-driven software platform that helps academic researchers recruit participants for research studies more efficiently using social media, software, and machine learning. BuildClinical utilizes study-specific advertisements to engage participants on digital platforms such as Facebook, Google, WebMD, etc., and redirect them to a study-specific landing page should they click it. On the landing page, the person can complete an online pre-screen questionnaire that gets routed into BuildClinical's platform. BuildClinical's Secure Socket Layer (SSL) software, which encrypts all inputted information, keeps participant information private and HIPAA compliant. BuildClinical's backend servers are stored in the USA at some of the most secure data centers in the world. The study team will access BuildClinical's platform to review and select qualified screening participants for additional screening. Interested individuals may then choose to enroll in the study by completing Informed Consent and HIPPA prior to scheduling a baseline lab or virtual session.

We have included the BuildClinical advertisement materials, pre-screening questionnaire, and study information landing page design and

IRB NUMBER: 10581
B NUMBER: 10581
IRB APPROVAL DATE: 02/14/2022
PROVAL DATE: 09/13/202112

content.[Inclusion/Exclusion criteria](#)

Inclusion criteria:

- (1) Ages 18 to 26;
- (2) Currently smoke cigarettes "somedays" or "everyday";
- (3) Started smoking "somedays" or "everyday" in the past 12-months or more than 12 months ago.
- (4) A strong preference for menthol or non-menthol cigarettes (i.e., smoke one type $\geq 80\%$ of the time).
- (5) Able to read and understand the informed consent
- (6) Willingness to abstain from nicotine containing products or other combustible products (e.g., smoked cannabis) for at least 12 hours prior to each in-person or virtual laboratory visit (confirmed by CO $\leq 8\text{ppm}$ for each in-person study visit in Phase 1). Will be rescheduled once if CO is not within acceptable range.

Exclusion criteria:

- (1) Current use of nicotine replacement therapy (NRT);
- (2) Currently pregnant or planning to become pregnant, or breast feeding (verified by pregnancy test at each study visit/session);

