Primary Outcomes: **(a)** the absolute reinforcing value (ARV) of menthol cigarettes from Visit 1, **(b)** the relative reinforcing value (RRV) of menthol cigarettes from Visit/Session 3 based on Choice Task responding; **(c)** RRV of own vs experimental brand based on price elasticity. ARV of menthol cigarettes will be operationalized as between subject differences in subjective ratings of menthol vs non-menthol cigarettes (satisfaction, reward, craving reduction, physical sensations) during the ad libitum smoking Visit. RRV will be measured by evaluating motivation to “work harder” for menthol versus non-menthol cigarette puffs or for one’s own brand from Visit 3. This is operationalized by the highest trial (breakpoint) that a participant successfully works for a menthol vs nonmenthol cigarette puff (or for their own vs experimental brand). Higher values reflect greater RRV of menthol cigarettes relative to non-menthol cigarettes (or their own brand vs the experimental brand. RRV of own vs experimental brand will be operationalized as cross-price elasticity of demand which measures the responsiveness of the quantity of experimental cigarettes that are self-reported to changing prices of the preferred cigarette brand.

Secondary Outcomes: **(a)** Total number of responses for the menthol versus the non-menthol-cigarette on the choice task **(b)** CO boost; and **(c)** puff topography (number of menthol versus non-menthol cigarette puffs consumed, number of minutes smoked, interval between puffs). Exploratory analyses will compare ARV and RRV.

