A 2 (menthol preference) X 2 cigarette type (usual brand versus experimental brand) mixed ANOVA will be conducted to examine main effects and interactions on the outcomes of interest. Models will examine cigarettes per day (CPD), nicotine dependence, race/ethnicity, gender, and age of smoking onset as potential covariates. Factors related to Phase 1 drop-out will be examined as potential covariates. If nicotine and CPD are collinear, the most significant predictor of the outcome will be retained in the model. Significant interactions will be followed up with individual contrasts of cell means using Fisher’s Least Significant Difference tests. In exploratory analyses, a 2 (menthol preference) X 4 (race/ethnicity: White, Black, Other, Hispanic) between-subjects ANOVA and a 2 (menthol preference) x 2 (gender) between subject ANOVA will be conducted separately for the BL Visit to evaluate differential reactions to own brand cigarette smoking by race/ethnicity and by gender. Comparison of own brand/usual brand and experimental cigarette ratings will also be made to determine the perceived similarity of the experimental cigarette to one’s own brand and as a function of gender and race/ethnicity. NOTE: We expect that ratings of appeal/reinforcement for the experimental cigarettes will be lower than ratings of appeal for usual brand. Ratings of experimental cigarettes will be examined as a potential covariate in Aim 3 models. Age of smoking initiation will also be examined as a potential covariate. Covariates with $p < .05$ will be retained in final models.

Phase 2/Aim 2 Analyses

Primary Outcomes: (a) within-day subjective response (craving reduction, satisfaction, psychological reward, physical sensations like throat grab) to the most recent cigarette smoked (menthol vs non-menthol); (b) betweenday subjective response.

Secondary Outcomes: (a) Aggregate ratings of subjective response (over the course of 14 days) by baseline menthol brand preference (at the person-level, rather than by day); (b) changes over the course of days (creating an average change score for each person); (c) within-person variability by calculating the standard deviation of daily cigarette reward, satisfaction, craving reduction, and throat hit ratings for each person; (d) cigarettes per day (within-day, over days); and (e) craving intensity (within-day, over days).

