This is a low-risk observational study and we do not anticipate any Serious Adverse Events. Because a Data and Safety Monitoring Board is only required for higher risk and/or multisite studies, and the proposed research is a single site study with minimal risk, a formal Data and Safety Monitoring Board formed is not required. We do, however, have a detailed data and safety monitoring plan. Adverse events will be assessed by research personnel at each study visit via participant self-report and managed immediately. All serious adverse events will be reported to the OUHSC IRB.

We will monitor for risk of using cigarettes by screening participants via self-report for general medical precautions (pregnancy, cardiovascular disease). The most likely adverse event (potential for nicotine overdose) is anticipated to be rare (< 1%) and mild (nausea, headache) and will be handled quickly (i.e., advice to participant to reduce or eliminate cigarette use). The PI will be available for any questions that participants may have about smoking, or smoking cessation. Participants will be given contact numbers of the laboratory and PI. Any adverse events, breaks of confidentiality, or any other data or safety issues that arise will be discussed immediately with the PI ([name]). [name], or a delegate (Project Manager) will be responsible for completing an Adverse Events Form should an event occur. The Adverse Events Form will be reviewed by the PI and will report Serious Adverse Events to the OUHSC IRB within 24 hours of having received notice of the event. [name] will gather any information needed to investigate the event and to determine subsequent action. Any subsequent action will be documented and reported to the OUHSC IRB.

Potential benefits of the proposed research to participants

The participants may benefit directly through increased understanding of factors underlying uptake, appeal, and use of menthol cigarettes, which is linked to smoking progression and poor cessation outcomes. This study is designed to answer important questions about factors that promote tobacco use behavior with the ultimate goal of informing prevention and regulatory decisions about menthol cigarettes and other flavored tobacco products. Improved regulation could ultimately help deter tobacco use among the larger population of young people, thus decreasing overall rates of tobacco-related morbidity and mortality, including those that stem from tobacco use and dependence.

References

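### Aim 1 compares self-selected menthol and non-menthol smokers, yet only an outcome p-value decides whether gender, race/ethnicity or age of onset is adjusted for, so an imbalanced, weakly prognostic confounder can be dropped

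*Combined protocol and SAP*

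**What the plan says.** All references are to the combined protocol and SAP.

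- **How the groups arise.** Under Inclusion criteria, participants must have "A strong preference for menthol or non-menthol cigarettes", so group membership is the participant's own choice. The Data Safety Monitoring Plan states: "This is a low-risk observational study".
- **What is compared.** The Study Objective predicts that, "compared to nonmenthol smokers, menthol smokers will show greater appeal/reinforcement, both in the laboratory and via EMA". For the primary absolute reinforcing value (ARV), Phase 1/Aim 1 Analyses states: "ARV of menthol cigarettes will be operationalized as between subject differences in subjective ratings of menthol vs non-menthol cigarettes".
- **How covariates enter Aim 1.** The same section says: "Models will examine cigarettes per day (CPD), nicotine dependence, race/ethnicity, gender, and age of smoking onset as potential covariates". It closes with "Covariates with $p < .05$ will be retained in final models". The only other retention rule there concerns cigarettes per day (CPD) and nicotine dependence: "If nicotine and CPD are collinear, the most significant predictor of the outcome will be retained in the model".
- **What else the Aim 1 section offers.** Exploratory ANOVAs at the baseline visit cross menthol preference with race/ethnicity (four levels) and, separately, with gender. Neither carries a p-value condition.
- **Phase order.** A sentence at the end of Phase 2/Aim 2 Analyses adjusts for the order of the study phases, with no p-value condition.
- **Aim 3.** Baseline outcome, gender, race/ethnicity and age of onset are controlled in Step 1. The p < .05 sentence is then repeated, with no word on whether Step 1 terms are exempt.

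**The concern.** Nothing in the design balances the two groups, so adjustment has to carry the between-group comparison. The bias from leaving out a covariate is roughly its difference between groups times its effect on the outcome. A significance test against the outcome sees only the second factor, and only with the power that 250 participants give. A variable with a clear group difference and a small effect can fail the test, leave the model, and pass its share of the difference to menthol preference.

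The plan also does not say how the p-value is obtained: each covariate alone, each with menthol preference in the model, or all together. Two analysts could reach different final models from the same data.

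At stake is the Aim 1 menthol-preference effect, including primary ARV. It could keep bias from variables the study has already measured.

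**Working it through.** **Inputs.** From the documents: 125 per group and retention at p < .05. The documents give no group imbalance, covariate effect, screening method, significance level for the menthol test or power calculation, so there is no stated figure to reproduce. Everything else is assumed: outcome residual SD 1, no true menthol effect, a two-sided 5% test and complete data.

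**What the rule can detect.** With menthol and one covariate in the model, df = 250 − 3 = 247. A covariate is kept if its sample partial correlation is at least t/√(df + t²) = 1.97/√(247 + 3.88) = 0.124. A slope of 0.10 per SD corresponds to a correlation of 0.10/√1.01 = 0.0995, below the threshold, so it is usually dropped. A slope of 0.20 gives 0.20/√1.04 = 0.196, so it is usually kept.

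**Bias if dropped.** Bias = slope × imbalance. One covariate at slope 0.15 and 0.3 SD apart leaves 0.15 × 0.3 = 0.045 SD. Three at slope 0.10 and 0.6 SD apart, all dropped, leave 3 × 0.10 × 0.6 = 0.18 SD. The unadjusted standard error is √(2/125) = 0.126.

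**Simulation.** Screen at p < .05, refit with the covariates kept, then test menthol. There were 10,000 runs per row (Monte Carlo error 0.2–0.35 points) and 4,000 for the last two rows (0.3–0.5 points). Imbalances all push the same way.

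| Setting | One at a time, menthol not in model | Joint, menthol in model |
|---|---|---|
| 1 covariate, 0.3 SD apart, slope 0.15 | 5.3% | 5.8% |
| 1 covariate, 0.6 SD, slope 0.15 | 5.4% | 7.3% |
| 3 covariates, 0.3 SD, slope 0.10 | 6.1% | 7.6% |
| 3 covariates, 0.3 SD, slope 0.20 | 5.1% | 5.9% |
| 3 covariates, 0.6 SD, slope 0.05 | 6.1% | 9.5% |
| 3 covariates, 0.6 SD, slope 0.10 | 6.8% | 13.7% |
| 3 covariates, 0.6 SD, slope 0.20 | 5.2% | 8.0% |
| 3 covariates, 0.6 SD, slope 0.30 | 5.2% | 5.3% |
| Gender, race/ethnicity, onset: moderate effects | 6.8% | 10.9% |
| Gender, race/ethnicity, onset: strong effects | 5.0% | 5.2% |

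Keeping all covariates gives 5.0–5.2%. The last two rows assume gender 45% v 60%, race/ethnicity 65/10/15/10 v 40/35/15/10 (3-df test) and age of onset 0.3 SD apart. Moderate effects are 0.2, 0.3/0.1/0.1 and 0.10 per SD; strong effects are 0.5, 0.8/0.3/0.3 and 0.30 per SD.

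Screening one at a time with menthol in the model behaves like joint screening when covariates are uncorrelated (13.7% at slope 0.10, three at 0.6 SD).

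**In the most extreme row** (13.7%), each covariate is kept 48% of the time (one at a time) or 35% (joint), with remaining bias of 0.05 or 0.08 SD. If one of the three imbalances is reversed, the rates are 5.3% and 9.6%.

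**Total error (root mean square) of the menthol effect.** One at a time compared with keeping all: 0.144 v 0.143 in that row, 0.134 v 0.143 at slope 0.05, and 0.133 v 0.132 for three at 0.3 SD and slope 0.10. Joint screening is worse in the extreme row: 0.174 v 0.143.

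**Price of keeping all.** The menthol standard error grows by √(1 + q), with q = k·d²/4 for k covariates d SD apart. For k = 3, d = 0.3: q = 0.0675, ratio 1.033. For k = 3, d = 0.6: q = 0.27, ratio 1.127.

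**The case against.** The strongest reply is that the harm depends on a screening method the plan leaves open. If each covariate is tested alone, the false-positive rate stays at about 5–7% and total error is practically the same as with full adjustment. That stands. Some bias remains in that case, but most of the damage belongs to joint screening or screening with menthol in the model.

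Second, the exploratory baseline-visit ANOVAs bring race/ethnicity and gender into the analysis of the visit where ARV is measured. This partly mitigates the gap. They take one factor at a time, leave out age of onset, are aimed at differential reactions, and do not adjust the primary model.

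Third, the top figure needs three covariates, each 0.6 SD apart, all weakly prognostic, all pushing one way and screened jointly. That also stands; no document suggests such a pattern.

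A reader might further infer that Aim 3 contradicts itself by controlling Step 1 terms and then screening them. The documents do not show this. The repeated sentence can be read as covering only added covariates; the Aim 1 section names one: "Ratings of experimental cigarettes will be examined as a potential covariate in Aim 3 models". Aim 3 is an ambiguity, not an error. The sentence also appears in Aim 2, but nothing here was computed for that model and no claim is made about it.

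**Conclusion.** The point holds for Aim 1 between-group menthol-preference effects, including primary ARV. The stated rule can drop a measured confounder because its outcome p-value misses .05, whatever its imbalance.

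The likely size is small: about 5–8% false positives against a nominal 5% with 0.3 SD imbalances. It is about 11% under joint screening with the assumed imbalances in gender and race/ethnicity and moderate effects, and about 14% only in the extreme case. All of this rests on assumed imbalances, slopes and group sizes.

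It would be wrong to conclude that the Aim 1 results are invalid or that important confounders will be lost. At slopes of 0.30, and in the strong-effects row, covariates are nearly always kept and the rate is about 5%. Purely within-person contrasts, such as the Visit 3 choice between menthol and non-menthol puffs, are not affected. This is a cheap improvement of minor to moderate severity.

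**What to change.** In Phase 1/Aim 1 Analyses, for between-group menthol-preference effects only, replace the p < .05 sentence with: *Gender and race/ethnicity (White, Black, Other, Hispanic) will be included regardless of p-value.*

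Define age of smoking onset; the section uses both onset and initiation. State in advance, with a causal rationale, whether it, CPD and nicotine dependence are in the primary model, and show the other choice as a sensitivity analysis. Each may be a confounder or a consequence of menthol smoking, so none should be forced in without that reasoning. This replaces choosing between CPD and dependence by significance.

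Confirm that the phase-order adjustment stated under Aim 2 also covers Aim 1.

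Optional clarification in Phase 3/Aim 3 Analyses: *Step 1 covariates are kept regardless of p-value and the covariate set is identical across steps.* Mediation is judged by the change in the menthol coefficient, which is hard to read if the adjustment set also changes.

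Cost: wording only, no new data. Gender and race/ethnicity use 1 + 3 = 4 degrees of freedom. The menthol standard error widens by about 3% for three covariates 0.3 SD apart and about 13% for three at 0.6 SD.

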to start time). The participant will attend an initial baseline visit, where informed consent will be completed and a baseline experimental visit of ad libitum smoking of one's preferred cigarette brand, and two additional visits later. The \geq 12-hour abstinence requirement was chosen because it controls for recent smoking exposure and produces optimal levels of smoking motivation that are sensitive to the experimental manipulations⁷ including the paradigm used in the current proposal, and prevents greater attrition and non-compliance relative to more prolonged periods.¹⁵⁷ Participants will be compensated \$45 for each in-person laboratory smoking visit in which they are eligible, or \$25 for Visit 1 if they are deemed ineligible. Participants will also be compensated \$35 for completing the baseline survey. Individuals will be compensated \$10 for each in-person visit (up to \$30).

Following are the standard procedures that have been adopted for the HPRC and OUM/OUHSC for all studies that will be facilitated in-person and would be utilized for this study in response to COVID-19.

PROCEDURE:

1. Employees will comply with all OUHSC COVID related policies and procedures as currently exist and as are revised in the future.
2. Efforts will be made to minimize face-to-face time with participants. When possible, consents will be sent to participants at their homes and reviewed by phone or zoom, as available. Additional items, including pregnancy tests, will also be shipped to the home, and reviewed over phone or zoom, when possible.
3. During scheduling, participants will be asked to wear a mask, if they have one available, to their appointments. For participants who do not have access to a face mask, they will be told that one will be provided. They will also be asked the questions from the OUM/OUHSC COVID19 Questionnaire (see attached in "Other Documents"). If the patient is symptomatic or has known direct contact with a person with COVID-19 they will be asked to consult with their PCP prior to re-scheduling their visit.
4. Participants will be instructed to call from their vehicle upon arrival for their appointment to prevent participants from congregating in the waiting room. They will also be verbally asked if any of their answers from the COVID-19 questionnaire have changed since their original completion. If the patient is symptomatic or has known direct contact with a person with COVID-19 they will be asked to reschedule their appointment.

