Phase 2 will examine the subjective effects (appeal) of menthol vs. non-menthol cigarettes (own brand) as they occur in the participant's natural environment. To achieve this aim (objective), participants will engage in 14 days of twice-daily ecological momentary assessment (EMA). Following Phase 1 (if recruited during normal operating procedures), participants will complete 14 days of EMA of smoking behavior and subjective response (satisfaction, craving reduction, psychological reward, sensory effects like throat hit) twice a day, smoking as usual. NOTE: If participants are enrolled when there are COVID-19 restrictions on in-person data collection, they will begin the daily EMA after they complete the baseline survey, and before they attend the 3-person visit lab visits. Participants will answer a set of questions about their smoking behavior by responding to a series of survey questions that will be deployed on an app installed on their phone (or a study provided phone if their phone is not compatible with the app. The app is only available only on the Android platform). Phones will be mailed back to the study lab at the end of the 14day monitoring period using a pre-addressed stamped envelope provided by the study team. Prompts (e.g., notifications to the telephone) will be programmed to occur at random times within each of two 4hour time blocks, one corresponding to the morning and one the evening. Prompts will be programmed to coincide with respondents' sleep-wake cycle (i.e., the usual time they wake up and go to bed). Sleep/wake cycle will be collected at the baseline visit. At the completion of EMA, participants will be

asked to participate in a brief assessment to query about satisfaction with and reactivity to the EMA assessments. They will get paid \$15 for this survey. EMA entries are expected to last ~5 minutes (based on response times in prior studies). Participants who miss EMA surveys or the EMA reactivity survey will be given the opportunity to complete the surveys by invitation via REDCap.

Phase 3 Overview and Experimental Design

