Patterns of missing data, attrition rates, distributional properties of dependent and other measures, and correlations among all measures will be assessed. We will control for potential variables related to missing data and utilize multiple imputation methods (expectation maximization algorithm). Analysis of EMA data will use hierarchical linear modeling (HLM, which provides flexibility in handling missing data such that robust estimates can be obtained even when data are missing at random (MAR). Models for Aim 2 will examine effects of cigarette type (menthol vs non-menthol) at the day-level on predictions of subjective response (satisfaction, reward, craving reduction, physical sensations like throat grab) in that same smoking episode, and subjective response at time t (e.g., morning) predicting smoking behavior (number of cigarettes, any smoking, craving) occurring at subsequent points in time to determine the impact of subjective response on continued use by menthol status (controlling for cigarette consumption and subjective response from the previous report). A sub-group of respondents may have fixed (unchanging) ratings of subjective response over the course of 14 days, although this is unlikely given our pilot study data suggesting that daily subjective response varies significantly in this age group. We will examine baseline and daily factors that set “no changers” apart from those whose show fluctuations in subjective response. These factors will be used as covariates in models. Within-person slopes capturing associations between cigarette type and subjective response will be saved and used in Aim 3 regression models to predict 6-month smoking outcomes. Covariates with $p < .05$ will be retained in final models.

Analyses will control for the order in which study phases were completed (e.g., Phase 1 vs Phase 2 first).

Phase 3/Aim 3 Analyses

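### The lagged Aim 2 EMA model has no morning/evening term, so a daily pattern in ratings and smoking could pass for an effect of subjective response on later smoking

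*Combined protocol and SAP*

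**What the plan says.** The combined protocol and SAP, under Phase 2/Aim 2 Analyses, describes a hierarchical linear model with "subjective response at time t (e.g., morning) predicting smoking behavior (number of cigarettes, any smoking, craving) occurring at subsequent points in time". The stated purpose is to see how response affects continued use by menthol status. The model is fitted "controlling for cigarette consumption and subjective response from the previous report".

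Other Aim 2 adjustments are mentioned, but none is a clock-time or interval term:

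- Missingness: "We will control for potential variables related to missing data". The variables are not named.
- Flat raters: "We will examine baseline and daily factors that set “no changers” apart from those whose show fluctuations in subjective response". These factors become covariates but are not listed.
- Phase order: "Analyses will control for the order in which study phases were completed".
- Retention: "Covariates with $p < .05$ will be retained in final models".

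Phase 2 Overview and Experimental Design sets the timing. Prompts "will be programmed to occur at random times within each of two 4hour time blocks, one corresponding to the morning and one the evening", for 14 days. Missed surveys may be made up through REDCap, with no time limit stated.

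**The concern.** With one morning and one evening report a day, consecutive lags are of two kinds. Morning to evening is waking time; evening to next morning includes sleep. Opportunity to smoke therefore differs between the two. If ratings also differ between morning and evening, time of day is related to both predictor and outcome and confounds the lagged slope. The two lagged controls carry some information about time of day, but both are noisy, so they remove only part of it.

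This is the only Aim 2 model that predicts later smoking, and the protocol justifies EMA partly by its ability to sequence behaviour causally. A spurious lagged effect, in either direction, would weaken that claim.

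**Working it through.** The plan states no power, effect size or error rate for this model, so there is no figure to reproduce. The check asks what the model returns when response has **no** effect on later smoking.

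**Inputs from the documents.** 125 + 125 = 250 participants; 14 × 2 = 28 reports each. Each record needs the previous, current and next report, giving 26 records per person and 250 × 26 = 6,500 in all. The assumed completion rate is 23/28 = 82%. That survey count appears in the Compensation section as a bonus threshold and is borrowed here only as a plausible level.

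**Assumptions (not in the documents).** Morning ratings are higher by d = 0.1 or 0.2 within-person SD. Participants smoke 5 cigarettes from morning to evening and 4 or 3 from evening to morning, so D = 1 or 2. Counts have Poisson-like variance v equal to the average of the two means (4.5 or 4). Each report counts cigarettes since the last one.

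**Expected slope.** Code time of day as z = ±1/2, with variance 1/4. Current response contains +d·z, previous response −d·z, previous consumption −D·z and the outcome +D·z, each with independent noise. The fitted coefficient on current response is then

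slope = D·d / (4 + 2d² + D²/v)

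and its standard error is about √(s²/n), with s² = v + D²/(4 + 2d² + D²/v).

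| d; cigarettes | Slope | SE, n = 6,500 | Slope/SE | Rejection at 5% |
|---|---|---|---|---|
| 0.1; 5 v 4 | 0.10/4.242 = 0.024 | √(4.736/6,500) = 0.027 | 0.87 | 14% |
| 0.1; 5 v 3 | 0.20/5.020 = 0.040 | √(4.797/6,500) = 0.027 | 1.47 | 31% |
| 0.2; 5 v 4 | 0.20/4.302 = 0.046 | √(4.732/6,500) = 0.027 | 1.72 | 41% |
| 0.2; 5 v 3 | 0.40/5.080 = 0.079 | √(4.787/6,500) = 0.027 | 2.90 | 83% |

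At 82% completion with reports missing independently, about 6,500 × 0.82³ = 3,584 records remain. The ratios fall to 0.65, 1.09, 1.28 and 2.15, and rejection to 10%, 19%, 25% and 58%.

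**Simulation.** Null simulations of the same four settings gave 17-78% false positives with complete data and 9-57% at 82% completion, with spurious slopes of about 0.02-0.08 cigarettes per SD. The hand calculation agrees. With a morning/evening indicator in the model, rejection returned to roughly 5%.

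**Check on a standardised scale.** A separate within-person regression with cluster-robust errors (150 runs per setting, complete data) used evening-minus-morning shifts in SD units for ratings and smoking:

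- no shift: 5% false positives;
- 0.2 and 0.2: 12%;
- 0.2 and 0.5: 38%, mean slope −0.020;
- −0.2 and 0.5: 43%, mean slope +0.023, so the sign follows the direction of the rating shift.

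Across all settings, including 82% completion, adding the indicator gave 3-10%, with mean slopes of about zero.

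**Comparison by menthol status.** When both groups share the same daily pattern, the response-by-menthol interaction rejects 3-8% of the time, close to nominal.

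**Elapsed time.** With each prompt random in a 4-hour block, the gap between a day's two prompts can vary by ±4 hours, an 8-hour range. The effect of that variation was not simulated.

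**The case against.** - **The lag may be meant as morning to evening only.** Morning is the plan's example of time t. With that restriction time of day is constant and the bias disappears. But it is only an example, and the outcome is placed at later time points in general, so the restriction is not stated.
- **The unnamed daily factors could include time of day.** They are aimed at people with flat ratings, and the p < .05 rule could drop any such term. This does not close the gap.
- **The pattern is assumed.** This stands. No document gives a morning/evening difference in ratings, cigarettes per interval, or the recall window of the cigarette item. A reader might cite the laboratory abstinence rule, chosen because "it controls for recent smoking exposure and produces optimal levels of smoking motivation", as evidence that morning ratings run higher. It concerns CO-verified abstinence of at least 12 hours before a visit. EMA participants smoke as usual and rate their most recent cigarette, which need not be the first after waking.
- **The effect is small and the analysis secondary.** This also stands. Cigarettes per day and craving are secondary Aim 2 outcomes; both primary outcomes are subjective response. The slopes carried into Aim 3 link cigarette type to response and come from a different model.
- **A reader might infer that the menthol comparison is biased.** With a shared daily pattern the interaction stays near nominal. Bias requires the groups' patterns to differ, and the documents give no evidence either way.

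**Conclusion.** The omission is real. As written, the pooled lagged effect can be falsely significant if both ratings and smoking vary by time of day. Under the assumed patterns the false-positive rate is about 17-78% with complete data and 9-57% at 82% completion, while the spurious slope is only about 0.02-0.08 cigarettes per SD of rating, against 3 to 5 per interval. These figures depend on the assumed shifts; with no daily pattern the error rate is nominal.

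It would be tempting to conclude that Aim 2 as a whole, or its feed into Aim 3, is compromised and that the plan must be corrected before use. The documents do not support that: no primary Aim 2 outcome and no Aim 3 input has been shown to be affected. This is a worthwhile, inexpensive improvement to a secondary analysis.

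**What to change.** Add a morning/evening indicator for the prompt to every lagged Aim 2 model and keep it regardless of the p < .05 rule. Where response is compared by menthol status, also include the indicator's interaction with menthol status, so that different daily patterns in the two groups are not read as different effects of response.

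Report morning-to-evening and overnight lags separately as a sensitivity analysis. Hours between reports may be added as a covariate; this is optional, since its benefit was not tested.

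The cost is one or two model terms. The prompt block is known by design, so no new data are needed. Making the same-day lag primary is not required: the indicator alone removes the bias, and the restriction would give up about half the transitions. Nor need the same-episode cigarette-type model change.
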